- 5. Clinician Knowledge and Attitudes Survey will be conducted to evaluate knowledge and skills related to the core behaviors, use of the tools and attitudes toward reducing cesarean delivery rates and implementing the intervention. This survey will no longer be administered.
 - a) The local site team will administer the survey to all clinicians' email addresses.
 - b) All clinicians with practicing privileges in the unit will be invited to participate and will be sent a hyperlink which will direct them to the Qualtrics survey.

- c) All surveys will be confidential.
- d) Consent text is available in the consent language attachments.
- e) Consent will be affirmed with an agreed statement, stating that moving forward with the survey, the participant is providing consent to participate.
- f) Participation will be voluntary and uncompensated for completion of multiple surveys.
- g) The survey will take no more than 15 minutes to complete.
- 6. Focus Group Discussions will be conducted to identify successes, challenges and other contextual factors that are impacting the implementation of the tools, identify adaptations that have been made, why they have been made and how to improve the tools or the implementation program. The majority of focus group participants will fill all three roles (i.e. super-users, champions and implementers). Consequently, focus group discussions will address issues relevant to all three roles. In the event that some individuals only have one role, separate role-specific focus groups will be conducted with these individuals (e.g. some individuals may be super-users but not champions or implementers). Focus group discussions will be held at beginning of project, project midline and end line at each study site leading to 3-5 focus groups per site.
 - a) Ariadne Labs Team will invite local site implementation teams to participate in focus group discussions.
 - b) Four to six members of the implementation team, champions and super users will be invited to participate in each focus group discussion.
 - c) A fact sheet, with all elements of informed consent, will be provided to participants during the scheduling process and at the time of the focus group.
 - d) Participants will be given the opportunity to ask questions and asked to confirm their consent to participate in the focus groups.
 - e) A semi-structured guide will be used. Focus groups that only include one role, will use a subset of questions from that guide.
 - f) These discussions will audiotaped.
 - g) Discussions will happen either in-person, at a location designated by the local site, or by video conference.
 - h) Participation will be voluntary and uncompensated for completion of multiple focus group discussions.
 - i) The audio files will originate with Ariadne Labs Project Team and the audio files will be transcribed.
 - j) These focus groups will not be anonymous, but no identifying information about the participants will be noted or recorded and all audio-recordings and transcripts will be kept confidential.
 - k) General themes from the interviews will be shared with each local site implementation team.
- 7. Patient Postpartum Surveys will be conducted by the local site team on the postpartum ward to provide an insight into patient experience of the tools.

- a. Convenience sampling will be used.
- b. Members of local staff will offer the survey electronically using an online survey service, Qualtrics, to all women who meet inclusion criteria while recovering from their delivery on the postpartum ward.
- c. The survey will be administered daily on a tablet device which will be offered to postpartum women by local staff.
- d. Any women who have experienced an intrapartum, stillbirth or neonatal death will not be asked to complete this survey.
- e. The survey will be completed once per eligible postpartum woman.
- f. There will be no incentives presented to postpartum women or surveys administered after discharge form the postpartum ward.
- g. Consent text is detailed in the consent language attachments and postpartum women will have the opportunity to ask questions to local staff prior to proceeding with completion of the survey.
- h. Consent will be affirmed with an agreed statement, stating that moving forward with the survey, the participant is providing consent to participate.
- i. Participation is voluntary and uncompensated, and women may stop taking the survey at any time.
- j. The survey will last no longer than ten minutes.
- k. Survey data will be analyzed and reported in aggregate on a monthly basis.
- l. Demographic data will be collected to assess the impact of the tools on different groups of women.
- m. Demographics that will be collected include: age, race/ethnicity, education, and parity.
- n. Any demographic data that is collected will not be shared unless there are at least five individuals in that category.
- 8. Patient Postpartum Interviews will be conducted by study team on the postpartum ward to provide an insight into the patient's care experience. Interviews will be conducted during the final month of data collection. Patients will also be screened to participate in interviews during the final month of data collection.
 - a. Convenience sampling will be used.
 - b. Members of the study team will offer patients the option to complete an interview and/or survey to all women who meet inclusion criteria while recovering in the postpartum ward. This is a one-time interview. There will be no invitations presented to patients after the patient has been discharged from the postpartum care unit.
 - c. Any women who have experienced an intrapartum, stillbirth or neonatal death will not be asked to complete this interview.
 - d. Participation is voluntary and uncompensated, and women may stop the interview at any time.
 - e. The interview will last no longer than fifteen minutes and collectively no more than 30 minutes if completed with a survey.

- f. One-to-one semi-structured interviews will be conducted by the Ariadne Labs Study Team and will be audio recorded.
- g. The audio files will originate with Ariadne Labs Study Team and the audio files will be transcribed.
- h. No identifying information about the participants will be noted or recorded and all audio-recordings and transcripts will be kept confidential.
- i. Interview will be analyzed and reported in aggregate by the Ariadne Labs Study Team.
- j. Demographic data will be collected to assess the impact of the care on different groups of women.
- k. Demographics that will be collected include: age, race/ethnicity, education, and parity.
- l. Any demographic data that is collected will not be shared unless there are at least five individuals in that category.
- m. If a patient participant completes both the survey and the interview, a code will be place on the interviewer's questions sheet and the survey which will link the demographic information. This is to avoid the participant having to complete this section twice. Demographic questions will mirror those presented in the patient survey.
- 9. Patient Level Data will be collected from patient records through a partnership between the Ariadne Labs and each local site team.
 - a) Patient record data will be extracted from the medical record system by the data and quality team at each local site.
 - b) The indicators that will be collected and analyzed for the project have been identified based on the measures used for other cesarean birth reduction projects and the measures of greatest interest to site leadership (see Appendix 3 for more details).
 - c) The Ariadne Labs Project Team will support each local site team to design a system to extract any data required for the project that is not currently being regularly collected.
 - d) All data will adhere to data protection agreements as described in Section 8.
- 10. Hospital Consumer Assessment of Healthcare Providers and Systems (HCAHPS) survey data will be shared with Ariadne Labs by site's study teams.
 - a) HCAHPS is a standardized, publicly reported survey of patients' perspectives of their hospital care and experience. All sites / hospitals are required to collect HCAHPS by the Centers of Medicare and Medicaid Services (CMS). The data from the survey will be used to allow study staff to better understand the patient experience in aggregate and compare with the patient surveys.
 - b) HCAHPS survey report will be shared securely with Ariadne Labs via email.
 - c) The survey reports will be sent on a quarterly basis including the quarter before launch as baseline data.

- d) This information does not contain any protected health information and displays quantitative data in aggregate.
- e) The survey is a standardized, publicly reported survey of patients' perspectives of their hospital care and experience. All sites / hospitals are required to collect HCAHPS by the Centers of Medicare and Medicaid Services (CMS). However, Ariadne Labs will only be sent HCAHPS reports specific to the Obstetrical unit.
- f) The HCAHPS reports are a general hospital quality metric captures that Ariadne Labs will use to compare to the results of the patient postpartum surveys.

IV. Analysis

The Ariadne Labs Project Team will analyze all data with the goal of addressing the specific aims and endpoints associated with each data source. A thorough statistical analysis plan and table shells will be drawn up before the final data analysis, but at a minimum it will include both quantitative and qualitative approaches, as well as specific attention to longitudinal changes in endpoints over time.

Quantitative approaches will include basic descriptive statistics such as means, percentages, and standard deviations over time. Because this study is not designed as a test of effectiveness and because our study populations will not be representative, no statistical tests for causal inference are anticipated. Analyses will be performed in SAS 9.4 or equivalent platform.

Qualitative approaches will include rapid thematic analysis of the qualitative sections of the observation form, the weekly coaching calls, clinician interview transcripts and focus group transcripts. Thereafter, all interviews will be transcribed and could be used for secondary analysis with data from other sites. This secondary analysis would be coded thematically using QSR NVivo or equivalent program qualitative analysis software to identify commonalities and differences. Secondary analysis of the qualitative fields from observation forms used in the quality improvement program at South Shore may be conducted at a later date to identify lessons for key implementation lessons for South Shore and future sites.

V. Outputs

The research evaluation will create the three key outputs:

- 1. Improved versions of the tools and implementation package that could be applied to successfully implement the program more broadly in the future.
- 2. Peer-reviewed publications co-authored with local site teams describing the feasibility and acceptability of the intervention and qualitative experiences of implementation.
- 3. White paper on generalizable lessons for implementation of solutions to address clinical complexity in childbirth.

5. Benefits

Possible benefits of participating in the quality improvement program are described as below:

1. Clinician Participants

As a result of participation in the quality improvement program, clinician-participants may experience improved team communication, greater reliability and accuracy for decisions making at key moments related to either admission or labor and delivery at their site.

2. Patient Participants

As a result of participation, laboring women may feel their preferences were reflected in the care they received, they were involved in key decisions and have a better experience of childbirth.

There are no benefits of the research project to either the clinician participants or the patient participants. However, insights gained from this program evaluation may contribute to the development of new improved methods of clinician-patient communication and scalable implementation lessons to support the spread of the program to other sites.

6. Risks

The quality improvement program focuses on processes of care and does not specify care plans and does not include any treatment-decision directives. All guidance conforms with evidence-based and nationally endorsed guidelines from obstetrics professional organizations, including the American College of Obstetricians and Gynecologists, the Society for Maternal-Fetal Medicine, the American College of Nurse-Midwives, and the Association of Women's Health, Obstetric and Neonatal Nurses.

For clinician participants, attending trainings, using the tools and being observed are part of the hospital's quality improvement process, so any risks would be associated with that effort and not the research. For patient participants, it is possible that the quality improvement program could be associated with a rise in complications associated with vaginal delivery, including 3rd/4th degree perineal lacerations and postpartum hemorrhage. Patients may also feel uncomfortable with having their care observed or with being explicitly included in the care team, especially during labor.

For clinician participants, the research components, voluntary participation in surveys, individual interviews and focus groups, carry very low risk of criminal or civil liability, financial standing, employability, insurability or reputation discomfort because the surveys, interviews, and focus groups do not contain sensitive topics. For patient surveys, there are no anticipated any risks to patients' criminal or civil liability, financial standing, employability, insurability, or reputation from taking the survey because the surveys do not contain sensitive topics.

7. Data Monitoring and Adverse Events

I. Data and Outcomes Monitoring

The principal investigator will assess the quality and completeness of patient level data regularly over the course of the study, and consistent problems will be identified and corrected as needed. Safety of subjects will be discussed actively and longitudinally as required during the period that the study is active, both with the participating site and also as an Ariadne Labs Project Team. Progress and potential safety or other concerns for subject will be discussed at protocol meetings to be held as needed during the duration of the protocol activity.

II. Adverse Events Reporting Guidelines

The proposed research will comply with the regulations set forth in 45 CFR Part 46, Protection of Human Subjects. The Ariadne Labs Project Team are educated on the protection of human research participants. They have been educated regarding HIPAA regulations and fully understand their responsibility to safeguard the personal health information of every participant involved in the research.

A communication plan has been developed to report adverse events for either patientparticipants or clinician-participants (see Appendix 3 for a list of possible adverse events). All events will be reported to the site investigator, who will then report all events to the Principal Investigator. The site investigator will be responsible for notifying their local IRB, and the principal investigator will promptly notify the HMS IRB in necessary instances, as determined by the Principal Investigator, within 5 business days. The Ariadne Labs Project Team will then meet, in conjunction with the site investigator, to discuss the adverse event and decide on strategies to avoid such events from recurring.

8. Data Security & Privacy

I. Data Security

All data will be stored on an Amazon Web Services server in a secure environment approved by Harvard University Information Technology (HUIT).

The following measures will be taken to ensure the data is stored securely: 1) all data will be encrypted in transit and at rest, 2) servers containing sensitive data will not be exposed to the internet and 3) access only to authorized personnel by role via proxy servers using AWS security groups and private subnets.

Users will be required to login and passwords will be a minimum of 8 characters and be alphanumeric. Vulnerability scanning will be performed daily and all user activity will be logged.

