- 4. Collection of preliminary data on the relationship between the tools and subsequent implementation on patient outcomes between the use of the tools and corresponding implementation with cesarean delivery rates

As the Quality Improvement Program progresses at each local site, we will collect additional data toward the above aims (Table 4). The three primary endpoints relate to the implementation of the intervention (Primary 1), its acceptability to various groups (Primary 2), and any unintended consequences, including adverse events that could impact patient safety (Primary 3). Additionally, cesarean delivery rates will be monitored at each site to identify any decline as a secondary endpoint. Since this is not an effectiveness trial, the study is not intentionally powered or designed to detect this reduction. The two exploratory endpoints will measure the specific adaptations of the program and any information on how the program succeeds or struggles in various contexts.

Table 4: Endpoints

Primary	1	High fidelity Implementation of the program
	2	Acceptability and feasibility of the program
	3	Patient safety
Secondary		Patient benefit, including program effectiveness at improving vaginal delivery rates
Exploratory	1	Adaptation of the program for improvement
	2	Determinants of how program successes and failures

The aims and endpoints will be measured with a variety of outcome measures, as shown in Table 5. Each aim maps to an endpoint, which is paired with a specific research question. The table also lists the specific measures and data sources we will use to address each question and the domains covered in each data source.

Table 5: Aims, endpoints, outcomes, data sources, and domains

Aim	Endpoint	Implementation question	Outcome measures	Data sources	Domains
1. Adaptation of the tools	Primary 1	How are the four core behaviors	Quantity and quality	Observations	Involvement of minimum team
and implementation strategy to optimize		implemented?	of core behaviors	Clinician Practice Surveys	Incorporation of woman's input
practice of the four			performed	Clinician Knowledge and	Precision of MFP distinction
behaviors				Attitudes Survey	Shared expectations
				Clinician Interviews	
				Patient Surveys	
	Primary 1	Are the tools implemented?	Quantity of tool use	Observations	Team huddle occurrence
				Clinician Practice Surveys	Whiteboard use
				Patient Surveys	Admission decision aid use
					Delivery decision aid use

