	Exploratory 1	What adaptations are made to the	Adaptations	Clinician Interviews	Site-specific adaptations
	intervention?			Implementation Focus Groups Discussions	Generalizable adaptations
2. Documentation of the feasibility and	Primary 2	Do clinicians find the tools acceptable and feasible to implement?	Clinician reports	Clinician Acceptability and Feasibility Surveys	Perceived value of behaviors, including collaboration
acceptability of the tools and implementation strategy to clinician and patient participants				Clinician Interviews	Ease of integration in workflow
	ian and nts			Implementation Focus Group Discussions	Adaptations and suggestions for improvement
	Primary 2	Are the tool and implementation	Patient reports	Patient Surveys	Role in care
		strategy acceptable to patients?			Communication with team
					Timing of care
	Primary 2	Do site teams find the tools acceptable	e Site team reports	Implementation Focus	Facilitators
		and feasible to implement?		Group Discussions	Barriers

Table 5: Aims, endpoints, outcomes, data sources, and domains

Aim	Endpoint	Implementation question	Outcome measures	Data sources	Domains
					Adaptations
					Adaptations
					Coaching and support
3. Detection of any harms	Primary 3	Has there been any harm to	Patient outcomes	Patient Level Data	Intervention rates
to associated with the tools or implementation		patients as a result of the tools and implementation strategy?	and care		Maternal morbidity and mortality
of the tools			processes		Neonatal morbidity and mortality
			Patient experience	Patient Postpartum Surveys	Role in care
					Communication with team
					Disempowerment
					Timing of care
4. Collection of preliminary	Secondary	Have there been any benefits to	Patient outcomes &	Patient Level Data	Intervention rates
data on the relationship between the tools and	n the relationship patients as a result of the tools care pro en the tools and and implementation strategy? juent	patients as a result of the tools	care processes		Delivery indications
subsequent				Admission timing	
implementation on patient outcomes					Admission indications
between the use of the			Patient experience	Patient Postpartum Surveys	Role in care
implementation with					Communication with team
cesarean delivery rates					Empowerment
					Timing of care
	Exploratory 2	What contextual factors may be	Contextual factors	Management Surveys	Other contextual factors

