related to cesarean delivery?			Site Implementation Team focus group discussions		

II. Research Eligibility Criteria

The following participants are eligible for this research project.

- 1. Clinician participants
 - i. Inclusion criteria
 - a) All clinicians (nurses, obstetricians and midwives as appropriate) who have practice privileges at each local site
 - ii. Exclusion criteria
 - a) None
- 2. Implementation Team participants
 - i. Inclusion criteria

a) Each local site implementation team which includes site champions, super-users and others who have been involved in the implementation of the process improvement program at each of the local sites

- ii. Exclusion criteria
 - a) None
- 3. Patient participants
 - i. Inclusion criteria
 - a) 18 years or older (15 years or older at St. Francis Hospital only)
 - b) Live birth (spontaneous or induction of labor)
 - Vaginally or
 - With an instrument (forceps/vacuum) or
 - Unscheduled cesarean delivery
 - ii. Exclusion criteria
 - a) Scheduled cesarean delivery
 - b) Experienced intrapartum, stillbirth, or neonatal death

At no time during the course of the study will the Ariadne Labs Project Team directly interact with patient participants for the purpose of data collection. All patient participant interaction will be the responsibility of local site staff.

III. Data Collection

We will use the data we collect to assess how the tools have been implemented, any adaptations that have been made to the tools for greater acceptability and feasibility of the program in order to deriver generalizable lessons for future implementation efforts. Data will be used to assess any unintended consequences and benefits of using the tools in clinical practice. The data collection approach is based upon the logic model we developed (Appendix 2) and Consolidated Framework for Implementation Research (CFIR).

All data collected will not include any identifiers for the participating clinicians or patients. Clinicians, the implementation team and patients will be invited to participate in surveys, interviews and focus group discussion as relevant. All participation will be voluntary. There will be no penalty for not choosing not to complete surveys or interviews.

- 1. Management Surveys will provide background information about contextual factors, including delivery volume, bed occupancy rates, nurse staffing levels and other organizational information.

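### The Section 4.II death exclusion is written for the whole research project, so if applied to the record data it sets the Primary 3 neonatal-death count to zero

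*Combined protocol and SAP*

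**What the plan says.** Section 4.II opens with a general scope: "The following participants are eligible for this research project". For patients it requires "Live birth (spontaneous or induction of labor") and, in exclusion (b), removes women who "Experienced intrapartum, stillbirth, or neonatal death". Neither rule is tied to a data source.

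In Section 4.I, Table 5 gives Aim 3 and Primary 3 the question of whether the tools or their implementation harmed patients. One domain, with Patient Level Data as its source, is "Neonatal morbidity and mortality". Appendix 3 names neonatal death among its example neonatal adverse-event indicators and requests it as a record field.

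Section 4.III describes each data source. Its opening says: "Clinicians, the implementation team and patients will be invited to participate in surveys, interviews and focus group discussion as relevant". Item 7, on postpartum surveys, repeats the exclusion: "Any women who have experienced an intrapartum, stillbirth or neonatal death will not be asked to complete this survey". Item 8 does the same for interviews. Item 9, Patient Level Data, describes who extracts the records and how the indicators were chosen. It does not mention eligibility, and it does not say whose records are included.

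**The concern.** Primary 3 is the endpoint on which the research would show harm from the program. Neonatal death is among the most serious outcomes on the list. An eligibility rule that removes women because of that outcome cannot sit beside an endpoint that counts it.

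Extraction is done by each site's own data team and, according to Table 1, starts in month 1. If one team or one analyst takes Section 4.II at its word, the neonatal-death result would read zero and could be taken as reassurance. If sites read the section differently, their rates would not be comparable.

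**Working it through.** The protocol gives no death rate, expected count or sample size for this endpoint, so there is no stated figure to reproduce. The check is a side-by-side reading with simple algebra.

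**Step 1. Scope of the rule.**
- Section 4.II: eligibility for the research project, with no limit by data source.
- Section 4.I, Table 5: Patient Level Data is a research data source for Primary 3.
- Read together, the rule reaches the record data.

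**Step 2. Effect on the neonatal-death indicator.** Consider singleton births among women for whom the tools are used, and set aside the other eligibility rules. Let N be the number of live births and D the number of neonatal deaths among them.
- No filter on birth outcome: rate = D / N.
- Exclusion (b) applied: rate = 0 / (N − D) = 0 for every D below N.

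The result does not depend on N or D, so no assumed rate is needed. Exclusion (b) is what removes neonatal deaths. The live-birth criterion acts on stillbirths.

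**Step 3. Effect on the other neonatal indicators.** Appendix 3 gives 5 examples: birth trauma, low Apgar at 5 minutes, intubation, NICU admission and neonatal death. Neonatal death is the 1 fixed at zero. For each of the other 5 − 1 = 4, let E be the number of events and E_d the number in babies who later died.
- No filter: E / N.
- Exclusion (b) applied: (E − E_d) / (N − D).

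The filtered rate is lower whenever E_d / D exceeds E / N, that is, whenever babies who died had the event more often than live-born babies overall. The protocol gives no values for these terms, so the size cannot be stated. Exclusion (b) concerns the baby's death and does not act on the maternal-death indicator.

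**Step 4. Was the rule meant for record data?**
- Items 7b and 8b offer the survey and the interview to women who satisfy the inclusion criteria. They are the only data-collection items that refer to those criteria.
- Items 7d and 8c repeat the death exclusion. Item 9 does neither.
- Appendix 3 requests Stillbirth, Neonatal death and Scheduled cesarean delivery. In an extract already filtered by Section 4.II, all 3 fields would be constant.

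This points to a rule meant for women approached in person.

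**Step 5. Does any sentence say so?** No. Sections 4.II, 4.III item 9, 4.IV and Appendix 3 contain no such limit. Section 3.IV defines the women for whom the tools are used, but does not tie that group to record extraction.

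**The case against.** The strongest reply is that this is an ambiguity with an obvious answer. The survey and interview items carry the criteria and the record-data item does not. The text closing Section 4.II is about direct interaction with patients. Asking for a neonatal-death field makes little sense if every such record is to be discarded. That stands as the more likely intent.

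The reply also holds that loss of the signal is remote. Table 1 classes record extraction as both quality improvement and research. Under Section 3.V the same project team analyzes the quality assurance record data, and Section 4.II does not govern that work. Section 4.IV promises a full SAP with table shells before the final analysis, which is a usual place to set denominators. This also stands, and it lowers the severity.

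It does not remove the defect. The intended limit has to be inferred, while the written scope is explicit. A later SAP would have to depart from the protocol's eligibility section to count these deaths.

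A reader might also take the reference in Section 7.II to adverse events in patient participants as proof that Section 4.II governs the records. It is not proof: Sections 5 and 6 use the same term for women in the quality improvement program, so its meaning is not fixed.

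**Conclusion.** The point holds as an over-broad eligibility rule. Applied to the record data as written, Section 4.II makes neonatal death, 1 of the 5 example neonatal indicators, zero by construction, and that part of Primary 3 cannot show harm. The consequence depends on one assumption: that a site data team or an analyst applies the section literally. Severity is modest, because the analysis is descriptive, the project team also receives the quality improvement data, and the rest of Section 4.III suggests a narrower intent.

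Some stronger readings are tempting and are not supported:
- **That neonatal deaths will be dropped, or that Primary 3 is biased.** The documents show a conflict in wording, not how the extract will be filtered.
- **That the stillbirth rules contradict Appendix 3.** Stillbirth is a requested field. It is not among the example indicators or named as a Table 5 domain, and a field can be requested in order to apply an exclusion.
- **That the age limit in Section 4.II contradicts the tool-use population in Section 3.IV, which has none.** A research group may be narrower than the group receiving the program.
- **That the secondary endpoint is wrongly defined.** The protocol says "cesarean delivery rates will be monitored at each site to identify any decline as a secondary endpoint" and gives no record-data denominator in item 9. That is missing detail, and nothing in the text shows which denominator was meant.

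**What to change.** 1. In Section 4.II, state that the live-birth criterion and exclusion (b) apply only to the Patient Postpartum Surveys and the Patient Postpartum Interviews.
2. In Section 4.III item 9, state that record data for Primary 3 are not filtered on birth outcome, so that neonatal deaths among the women for whom the tools are used under Section 3.IV are counted.
3. In the SAP, state the denominator for the secondary cesarean endpoint. The choice is left to the study team.

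The cost is a short protocol amendment with IRB review. Neonatal death is already a requested field, so the change needs no new data item. It involves no contact with bereaved women and leaves the program itself unchanged.
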